### **Both groups**

Following induction in both groups, the blood pressure and heart rate will be measured every one minute for the first 15minutes following the administration of either propofol or methohexitol, and all hemodynamic parameters (systolic blood pressure, diastolic blood pressure, heart rate) will be recorded on the data collection sheet.

Hypotension will be defined as a systolic blood pressure of less than 85 mmHg or greater than 30% decrease in the mean systolic blood pressure (as determined above), whichever is greater. If the patient develops hypotension with a systolic blood pressure of less than 85mm Hg during the 15 minutes following induction of anesthesia, the treatment algorithm outlined below will be followed (Eyraud et al., 1999; Mets, 2013):

One dose of phenylephrine will be administered if heart rate is 60 bpm or above, whereas 5mg of ephedrine will be administered if heart rate is below 60 bpm. The blood pressure will be rechecked 1 minute following, and the process repeated once or twice if necessary. If the

patient is still hypotensive following 3 total doses of vasopressors (phenylephrine and/or ephedrine), they will be considered to be in refractory hypotension and 0.5 Units of vasopressin will be administered. The blood pressure will be rechecked 1 minute following administration of vasopressin. If systolic blood pressure is still less than 85 mmHg, an additional 0.5 Units of vasopressin will be repeated once or twice as needed. Persistent refractory hypotension despite the aforementioned vasopressors will be treated with 4 micrograms of intravenous norepinephrine. All hemodynamic parameters for 15min following anesthetic induction will be recorded by the attending anesthesiologist.

Following anesthetic induction in both study groups, blood samples will be collected (as described above) at 3, 5, 10 and 15 minutes following anesthesia induction. The blood samples will be processed by dedicated research technician as described below.

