### **8.0      Subject Numbers and Statistical Plan**

#### **8.1      Number of Subjects**

The total sample size will consist of 120 participants (i.e., 60 per treatment arm). A sample size of 47 subjects per group will provide 90% statistical power to detect a difference of 0.3, between the proportion of subjects having at least one hypotension episode in the propofol group compared to the proportion in the methohexitol group, using a two-sided, chi-square test having a significance level of 0.05. However, we anticipate a drop-out rate as high as 20% for this study; therefore, we will enroll a total of 120 subjects.

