## 8.2 Sample size determination

The primary outcome of this two-arm trial is the proportion of subjects that have at least one hypotension episode within 15 minutes of administration of the randomized treatment medication. A hypotension episode is defined as having a drop in systolic blood pressure  $>30\%$  from baseline and/or having systolic blood pressure  $<85$  mmHg. Eyraud et al found 42 out of 51 subjects (0.82) had at least one hypotension episode using propofol (Eyraud et al., 1999). We expect our propofol proportion to be slightly higher due to our definition of a hypotension episode and our patient population. Further, we believe an absolute reduction of 0.30 in the proportion of subjects having at least one hypotension episode in the methohexitol group compared to the propofol group is clinically important. Although the randomization will be stratified by two factors (gender and drug type), to provide a conservative sample size estimate these factors were not taken into consideration for the power analysis because the correlation of these stratification covariates with the outcome would simply increase the precision, and hence, increase the power.

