## 8.3 Statistical methods

Primary analyses will invoke an intent-to-treat paradigm, wherein all randomized subjects are included according to their randomized treatment arm, regardless of actual treatment received, compliance, etc. Data will be summarized using descriptive statistics for continuous variables (mean, standard deviation, number of observations, and percentiles) and frequency statistics (frequencies and percentages) for categorical variables. Univariate and bivariate distributions will be inspected in order to address any missing data, inconsistent responses, outliers, and data entry errors. The sample size estimates have taken into consideration a participant drop-out of 20%; however, every effort will be made during the studies to minimize any drop-out. All hypothesis tests will be two-sided and analyses will account for the two randomization stratification factors of gender and inhibitor type. All analyses will be performed using SAS software, version 9.4 (SAS Institute, Inc., Cary, NC), R software, version 3.2.2 (R Foundation for Statistical Computing, Vienna, Austria), or Stata software, version 13 (StataCorp LP, College Station, TX).

For the primary outcome of the proportion of participants having at least one hypotension episode, log-binomial regression will be used to compare the propofol and methohexitol groups, adjusting for the randomization stratification factors of gender and inhibitor type. Because this is a prospective study, the log-binomial model allows us to estimate the risk ratio rather than the odds ratio while adjusting for covariates (Wacholder, 1986).

For secondary outcome of the proportion of patients experiencing refractory hypotension, the log-binomial model as described for the primary outcome will be used to compare the treatment groups. Poisson regression will be used to compare the two treatment groups, adjusting for the randomization stratification factors, with respect to the secondary outcomes of (a) the number of vasopressor doses (i.e., ephedrine, phenylephrine and vasopressin) administered per patient and (b) the number of hypotension episodes per patient over the first 18 after treatment initiation. In the event that there is an excess of zero counts, zero-inflated Poisson (ZIP) regression will be considered (Lambert, 1992).

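### The Poisson analyses of vasopressor doses and hypotension episodes allow for neither over- nor under-dispersion, so their usual standard errors can be wrong in either direction

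*Combined protocol and SAP*

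**What the plan says.** Section 8.3 gives one method for two counts, the vasopressor doses each patient receives and the hypotension episodes each patient has: "Poisson regression will be used to compare the two treatment groups, adjusting for the randomization stratification factors, with respect to the secondary outcomes". If there are too many zeros, "zero-inflated Poisson (ZIP) regression will be considered"; no criterion for excess is given. Later in 8.3 there is a general provision to inspect residuals and, where needed, transform the response. The section does not mention robust standard errors, a dispersion parameter or negative binomial regression, and does not say which type of standard error will be used.

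Section 7.2.2 (Both groups) fixes how the dose count arises. Treatment starts only when systolic pressure is below 85 mmHg. After a dose of phenylephrine or ephedrine, "The blood pressure will be rechecked 1 minute following, and the process repeated once or twice if necessary". A patient still hypotensive after three such doses moves to vasopressin, which may be given up to three times. The doses that 8.3 counts can therefore reach 3 + 3 = 6 in one sequence.

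On error level, 8.3 says "All hypothesis tests will be two-sided" and attaches no significance level. The figure 0.05 appears only in Section 8.1, for the primary power calculation.

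**The concern.** Poisson regression takes its standard errors from the assumption that variance equals mean. A stop-or-continue rescue rule does not produce such counts. It gives a block of zeros (patients never below 85 mmHg), a block of ones (prompt responders) and a tail of non-responders. A long tail pushes the variance above the mean. If most patients are treated and respond to one dose, the count is nearly constant and the variance falls below the mean. Neither contingency in 8.3 deals with this reliably: a zero-inflated model addresses surplus zeros only, and transforming the response does not correct a Poisson variance.

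Vasopressor doses are the first secondary endpoint in Section 1.3, and Section 12.2 makes less vasopressor use part of the case for methohexital. If the errors are too small, chance can look like such an effect. If they are too large, a real difference can be missed.

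**Working it through.** **The plan's own figure.** None is given for the count analyses. The primary figure reproduces. Section 8.1 states "A sample size of 47 subjects per group will provide 90% statistical power to detect a difference of 0.3". Section 8.2 cites a study in which "42 out of 51 subjects (0.82) had at least one hypotension episode using propofol" and expects a slightly higher rate, without a figure. Assuming 0.85 against 0.55 (mean 0.70):

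n = [1.96·√(2·0.70·0.30) + 1.2816·√(0.85·0.15 + 0.55·0.45)]² / 0.30² = (1.270 + 0.785)² / 0.09 ≈ 47 per group.

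Then 47/0.8 = 58.75, or 59 per arm (118 in all), against 120 planned. With 0.82 against 0.52, n is 50 and power at 47 is 88.4%. None of this involves the count models.

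**Model for the counts.** Let p be the share of patients with a count of at least 1, and r the chance that a further dose (or episode) follows. Then P(0) = 1 − p and P(k) = p·r^(k−1)·(1 − r), with the remaining mass at the cap.
- From the documents: cap of 6 doses (3 + 3), 60 per arm, two binary adjustment factors.
- Assumed: p, r, a single dosing sequence, and a cap of 4 episodes.
- The upper p of 0.82 borrows the cited episode rate. Rescue requires pressure below 85 mmHg, whereas an episode also includes a 30% fall, so the treated share should not exceed the episode rate.

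**Dispersion.** Without the cap, mean = p/(1 − r) and variance = p(1 + r − p)/(1 − r)², so

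φ = variance/mean = (1 − p + r)/(1 − r).

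φ = 1 only at r = p/2. Above that the count is over-dispersed, below it under-dispersed. The cap moves this point up slightly.

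**Effect on the test.** A nominal two-sided 5% Wald test with model-based errors has true size 2·[1 − Φ(1.96/√φ)].

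*Example, doses, p = 0.5, r = 0.5, cap 6.* The probabilities of 0 to 6 doses are 0.5, 0.25, 0.125, 0.0625, 0.0313, 0.0156 and 0.0156. Mean 0.984, variance 1.797, φ = 1.83. Then 1.96/√1.83 = 1.45, and size = 14.7%. The correct interval is √1.83 = 1.35 times as wide as the model-based one.

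**Check by simulation.** No treatment effect, 60 per arm, Poisson regression adjusted for two binary factors, 2,500 runs per setting:

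| Count | p | r | φ | Size, formula | Size, simulated model-based | Size, simulated sandwich |
|---|---|---|---|---|---|---|
| Doses | 0.5 | 0.2 | 0.87 | 3.6% | 2.9% | 4.8% |
| Doses | 0.5 | 0.3 | 1.13 | 6.6% | 6.1% | 5.0% |
| Doses | 0.5 | 0.5 | 1.83 | 14.7% | 14.8% | 5.5% |
| Doses | 0.5 | 0.7 | 2.60 | 22.4% | 22.0% | 5.0% |
| Doses | 0.82 | 0.3 | 0.68 | 1.7% | 1.2% | 4.6% |
| Doses | 0.82 | 0.5 | 1.20 | 7.3% | 6.8% | 4.9% |
| Doses | 0.82 | 0.7 | 1.65 | 12.8% | 13.1% | 4.7% |
| Episodes | 0.82 | 0 | 0.18 | 0.0% | 0.0% | 4.3% |
| Episodes | 0.82 | 0.2 | 0.46 | 0.4% | 0.3% | 5.0% |
| Episodes | 0.82 | 0.5 | 0.93 | 4.2% | 3.4% | 4.7% |
| Episodes | 0.67 | 0.2 | 0.65 | 1.5% | 1.2% | 5.2% |

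Across these settings, at 60 and at 48 per arm, sandwich and Pearson-scaled errors gave 4.3% to 5.7%. Separate runs with sandwich errors gave about 4% to 7%.

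**Extremes for doses, by formula.** p = 0.82, r = 0.2: φ = 0.47, size 0.4%. p = 0.4, r = 0.7: φ = 2.89, size 24.9%.

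**Episodes.** At p = 0.82 and r from 0 to 0.3, size by formula is 0.0% to 1.4%. At r = 0.2 the model-based interval is 1/√0.46 = 1.47 times too wide. This is not universal: at p = 0.52 and r = 0.5, φ = 1.49 and size is 10.9%.

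**The case against.** The strongest reply is that the plan has not chosen a wrong method; it has left a detail open. It never says model-based, it plans residual checks, and it holds a zero-inflated model in reserve for the case where many patients need no dose. That model does help. In null simulations (60 per arm, unadjusted, 600 runs), a two-part zero-inflated likelihood-ratio test cut the size from 20.8% to 7.0% at p = 0.5, r = 0.7, and from 15.3% to 8.8% at p = 0.5, r = 0.5.

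Part of this stands. The standard-error type is unspecified, and the large figures above are for plain Poisson. But model-based errors are what a Poisson fit ordinarily returns when nothing else is requested. The zero-inflated model is only to be considered, has no trigger, leaves some inflation, and splits the treatment effect into two parts. It cannot represent under-dispersion, because its variance is never below its mean.

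A reader might go further in three ways, none supported by the documents.
- *That the dose test must give too many false positives.* With no treated share or response rate stated, the direction is open; at p = 0.82, r = 0.3 the test is conservative. Between-patient variation in response would tend to raise dispersion, but the documents give no basis for its size, so it is left out.
- *That a stated 5% level is breached.* The level appears only for the primary calculation, "using a two-sided, chi-square test having a significance level of 0.05". Here 5% is a nominal yardstick.
- *That doses are correlated observations within patients, and that this invalidates the episode analysis too.* Each patient contributes one total, so the matter is dispersion, and episode counts with few repeats err on the conservative side.

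**Conclusion.** The point holds as a weakness of two secondary analyses. Given the rescue algorithm, Poisson variance would be right only near r = p/2, and 8.3 names nothing that secures valid errors elsewhere. For doses, with p of 0.4 to 0.82 and r of 0.2 to 0.7, a nominal 5% test has a true size of roughly 0.5% to 25%. For episodes at a rate of 0.82 with repeat probability up to 0.3, it is about 0% to 2%, with intervals that are too wide.

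The structural argument comes from the documents. The sizes rest on assumed p and r, a constant repeat probability, the caps, and model-based errors as the default. Confidence intervals are affected in the same way as tests. The primary log-binomial analysis and the sample size are not affected, and no multiplicity scheme or decision rule in the plan depends on these p-values. The change is worth making before the data are analysed, but it does not threaten the trial's main conclusion.

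**What to change.** In Section 8.3:
- Keep the log-link Poisson mean model, the adjustment for gender and inhibitor type, and the rate ratio for both counts.
- Prespecify robust (sandwich) or Pearson-scaled standard errors, naming one. Either corrects errors in both directions.
- Make the zero-inflated model a sensitivity analysis, not a replacement chosen after seeing the data.
- State the significance level, or nominal confidence level, for secondary outcomes.

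While editing that paragraph, reconcile the episode count with the rest of the protocol: its time window reads 18 with no unit, against 15 minutes elsewhere, and the number of episodes is not among the secondary endpoints in Section 1.3.

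The cost is a few sentences and one software option, with no extra patients or data. Dose intervals may widen, by a factor of about 1.35 at p = 0.5, r = 0.5; where counts are under-dispersed, intervals narrow.

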## **2.3 Study Rationale**

This study is being instituted to determine the hemodynamic stability of induction of anesthesia with methohexitol or propofol in patients presenting for elective surgery who were receiving ACEI or ARB therapy. In addition, we wish to determine whether there are any different effects of these induction agents on circulating neurohormones relevant to hemodynamic homeostasis, namely arginine vasopressin (AVP), Angiotensin II (All), and circulating norepinephrine (NE) and epinephrine (Epi).

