For secondary hemodynamic outcomes of systolic blood pressure, diastolic blood pressure and heart rate over the first 15 minutes after treatment initiation, the area under the curve (AUC) for each of these variables will be calculated using the trapezoidal rule. The AUC of each of these variables will be compared between the two treatment groups using linear regression models adjusting for the randomization stratification factors. A linear regression model also will be used to assess differences between the two treatment groups with respect to the duration (in minutes) of hypotension.

Blood will be collected at baseline, 3 min, 5 min, 10 min, and 15 min after treatment initiation to assess changes from baseline in AVP, AI, Epi and NE between the two treatment groups. For these continuous secondary outcomes collected longitudinally, linear mixed-effects models will be fit to compare the two treatment arms with respect to changes in these outcomes over time(Laird and Ware, 1982). The independent variables in the model will be treatment arm, time, the interaction of treatment and time, as well as the randomization stratification factors as covariates. From the mixed-effects models, contrasts will be constructed to test the hypotheses of interest with respect to changes over time in the outcomes. Linear mixed-effects models are an extension of ordinary regression models that account for the between- and within-subject correlation inherent in data involving repeated measurements per subject and allows for the variance-covariance matrix to be explicitly defined.

Following our assessment of the initial fit of the models, we will add covariates to the models that correspond to potential confounders to assess their impact, if any, on the treatment effects. Residual diagnostics will be assessed to determine the appropriateness of the model fit and, if necessary, transformations of the response will be used to meet modeling assumptions. Differences in means and associated confidence intervals (CIs) will be used to quantify the magnitude of the effects for continuous outcomes.

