## **10.0 Data and Safety Monitoring Plan**

### **10.1 Periodic evaluation of data**

We plan to perform an interim analysis of the data collected after every 30 patients enrolled in the study, until our sample size of 120 patients is achieved. We anticipate that patients receiving antagonists of the renin angiotensin aldosterone system will experience hypotension following the administration of propofol, although this is routine practice in anesthesiology without scientific literature to contraindicate practice. Our plan to treat hypotension with vasopressors is supported by the scientific literature(Mets, 2013), although we will modify our treatment plan accordingly if we deem that it is either causing hypertension or inadequate treatment of hypotension when it occurs.

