### **11.0 Risks**

The research requires the establishment of a second intravenous line following anesthetic induction. The use of an additional intravenous line is common anesthetic practice, although (as with any invasive procedure) there is the risk of bleeding, infection at the venipuncture site and infiltration of the intravenous catheter with the infusion of medications or fluids. In this study, the line will be used to draw blood samples, but following termination of the study protocol it will be used for the administration of standard fluids and drugs required for anesthetic care.

While there is currently no evidence to suggest that either randomization arm is harmful compared to the other, there is the risk that patients will be randomized to receive an induction drug that may potentially cause more hypotension compared to the other. We will perform interim analysis of our data and stop the study should we have reason to believe that one medication is causing significant harm compared to the other. Patients will be randomized to receive either propofol or methohexitol which both have the potential to cause hypotension.

Risks of propofol:

>10% incidence: low blood pressure (3%-26%), Injection site burning, stinging, or pain (18%), stop breathing for 30-60 seconds (adults 24%)

1% to 10% incidence: abnormal heart rhythm (1% to 3%), slow or fast heart rate (1% to 3%), cardiac output (volume of blood pumped by the heart per minute) decreased (1% to 3%);

Risks of methohexitol (frequency not defined but these complications are considered very rare since methohexitol is considered standard of care):

Sudden stop in blood circulation due to the failure of the heart, low blood pressure, shutdown of arteries and veins in the arms and legs, fast heart rate, agitation coming out of general anesthesia, headache, anxiety, restlessness, seizures, convulsion, injection site pain, abdominal pain, nausea or vomiting, blood clot in your leg that blocks one or more of your veins, breathing problems (stop breathing, bronchospasm, cough, labored breathing, hiccups, spasm of the vocal cords making it difficult to speak or breath, inadequate breathing).

One of three trained anesthesiologists will be administering each of these induction drugs, and has the expertise to anticipate and effectively treat each of these potential complications.

There is a possible risk of loss of confidentiality of health information.

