### **12.2 Potential Benefits to Others**

The results of this study will be used determine whether methohexitol is a safer drug to use in anesthetic induction of patients receiving ACEI or ARBs (by causing less hypotension and less administration of vasopressor drugs). If this is the case, it may contribute to changing standard anesthetic practice and improving patient safety.

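### The raw AUC for systolic pressure and heart rate lets readings above baseline cancel readings below it, and no between-arm analysis counts the high side

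*Combined protocol and SAP*

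**What the plan says.** Section 2.3 gives the purpose as "to determine the hemodynamic stability of induction of anesthesia with methohexitol or propofol". Under section 7.2.2 (Both groups), "the blood pressure and heart rate will be measured every one minute for the first 15minutes" after the study drug, and section 1.3 lists SBP, diastolic pressure and heart rate at one-minute intervals as secondary endpoints.

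For these three series section 8.3 specifies one between-arm analysis: "the area under the curve (AUC) for each of these variables will be calculated using the trapezoidal rule", and the areas are then "compared between the two treatment groups using linear regression models adjusting for the randomization stratification factors". The area is of the variable itself. It is not referred to baseline, and baseline is not named as a covariate. After the initial fit, "we will add covariates to the models that correspond to potential confounders to assess their impact", but those covariates are not named.

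The outcomes built on a threshold all look downward. They are at least one hypotension episode (primary), number of episodes, duration of hypotension and refractory hypotension. Vasopressor doses also follow low pressure.

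The high side appears elsewhere without an analysis:
- Section 2.1 expects methohexitol to raise heart rate.
- Section 10.1 would change the rescue plan "if we deem that it is either causing hypertension or inadequate treatment of hypotension when it occurs".
- Section 11.0 lists, among methohexitol's risks, "shutdown of arteries and veins in the arms and legs, fast heart rate". It also lists slow or fast heart rate for propofol, at 1% to 3%.

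**The concern.** Stability has two sides. A raw AUC divided by 15 minutes is a time-averaged level, so a patient who falls and then overshoots can have the same average as one who barely moves. Two stimuli that can push readings up lie inside the window: intubation, 3 minutes after rocuronium, and vasopressor rescue. If one arm overshoots more, its SBP or heart-rate AUC rises, and nothing in section 8.3 shows whether the rise came from shallower falls or from readings above baseline.

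For SBP the low-side outcomes give a partial check on the AUC. For heart rate there is none: the AUC is its only comparison, there is no threshold outcome in either direction, and a rise is expected in one arm. At stake is how the hemodynamic secondary results can be read.

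**Working it through.** **The plan's figures.** The documents give no mean, SD or expected difference for SBP or heart rate, so there is no AUC figure to reproduce. The stated primary sample size does reproduce. Taking 0.85 v 0.55 (an assumption consistent with section 8.2, which expects slightly more than 0.82 and a reduction of 0.30):

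n = [1.96·√(2·0.70·0.30) + 1.2816·√(0.85·0.15 + 0.55·0.45)]² / 0.30² = (1.270 + 0.785)² / 0.09 ≈ 46.9, so 47 per group. The AUC point does not touch this figure.

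**Why a raw AUC nets.** For a patient with baseline b followed for 15 minutes,

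AUC = 15·b + (area above b) − (area below b).

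Only the difference of the two areas enters the comparison.

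**Constructed traces, minutes 0 to 15 (all values assumed).** The trapezoidal AUC at one-minute spacing is the sum of the 16 readings minus half of the first and last.

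- Heart rate, b = 70. Flat: 15·70 = 1050.0. Swinging (70, 60, 52, 50, 50, 52, 55, 80, 95, 95, 90, 85, 75, 72, 70, 69): 1120 − 69.5 = 1050.5.
- SBP, b = 140. Dip and overshoot (140, 130, 110, 90, 80, 80, 95, 150, 165, 165, 155, 145, 130, 120, 110, 105): 1970 − 122.5 = 1847.5. Mild dip (140, 125, 110, 105, 105, 105, 110, 120, then 125 to the end): 1920 − 132.5 = 1787.5.

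The areas below and above use each reading's shortfall or excess against b, with the same rule.

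| Trace | AUC | Area below | Area above | Absolute deviation |
|---|---|---|---|---|
| Heart rate, flat | 1050.0 | 0 | 0 | 0 |
| Heart rate, swinging | 1050.5 | 101.5 | 102.0 | 203.5 |
| SBP, dip and overshoot | 1847.5 | 332.5 | 80 | 412.5 |
| SBP, mild dip | 1787.5 | 312.5 | 0 | 312.5 |

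The heart-rate AUCs are almost equal although one patient is flat and the other is not. For SBP the less stable trace has the higher AUC by 60, which is 80 more above baseline less 20 more below. The primary definition still separates the SBP traces: 70% of 140 is 98, and the first trace has four readings under it (90, 80, 80, 95) while the second has none.

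**Simulated arms (illustration only).** Assumptions: 60 per arm; baseline SBP 140 (SD 15); the same falls in both arms, averaging 25% at minutes 2–6 and 10% otherwise; reading noise SD 6. One arm gains extra pressure at minutes 7–12. The comparison is unadjusted.

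| Added pressure | Hypotension, each arm | Difference in AUC/15 | Runs with significantly higher AUC | Any reading >120% of baseline |
|---|---|---|---|---|
| 15 mmHg | 52% | 5.9 mmHg | 60% | 1% v 0% |
| 30 mmHg | 52% | 12.0 mmHg | 99% | 36% v 0% |

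At +15 mmHg the gain mostly offsets the residual fall of about 14 mmHg (10% of 140). At +30 mmHg a good part is overshoot. The raw AUC reports both simply as a higher level.

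**Sensitivity.** With an assumed overshoot of 20–40% at minutes 5–8 in one arm, the share of the AUC gain lying above baseline was 19–48% under one assumed recovery shape and 4–19% under a slower one. Detectability also depends on the model. For AUC/15 differences of 5.2, 7.8 and 10.4 mmHg, with 48 per arm (60 less 20% drop-out) and an assumed unadjusted SD of 16, the standard error is 16·√(2/48) = 3.27. Power ≈ Φ(difference/3.27 − 1.96) = 36%, 67% and 89%. With baseline adjustment it was 87–100% in one set of assumed traces, but section 8.3 does not name that adjustment.

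**The case against.** The strongest reply is that the trial is about hypotension. The hypothesis and Aim 1 say so, and five planned outcomes measure it. An overshoot cannot undo an episode that has occurred or a dose that was given. Section 8.3 assigns the AUC no favourable direction, and all tests are two-sided. Percentiles are planned for continuous data, and the interim reviews look at blood pressure, heart rate and vasopressor use, so high readings might be noticed. All of this stands. It confines the point to secondary outcomes, but it does not supply a between-arm analysis of the high side: the descriptive summaries are not tied to one, and section 10.1 gives no threshold or count.

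Three stronger readings are tempting and are not supported.
- **That hemodynamic stability goes unmeasured.** The low side is measured thoroughly; the gap is the high side.
- **That the AUC is tilted toward methohexitol.** In the simulations the overshooting arm is an input. If propofol patients need more rescue, as the hypothesis implies, overshoot after rescue could raise the propofol AUC instead. Section 11.0 lists fast heart rate for both drugs, and section 2.1 does not predict SBP above baseline with methohexitol.
- **That a safety claim would rest on hypertension counted as benefit.** Section 12.2 asks "whether methohexitol is a safer drug to use in anesthetic induction", and the same sentence ties this to less hypotension and less vasopressor use, not to the AUC.

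**Conclusion.** The point holds as a limited weakness in the secondary analyses. The raw AUC cannot separate better maintenance from overshoot in either arm, and no planned between-arm analysis counts high SBP or high heart rate. It matters most for heart rate.

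That netting occurs is arithmetic and needs no assumption. Its direction and size in this trial are unknown, because every mmHg figure, percentage of patients and power value for the AUC above rests on assumed means, SDs and trace shapes. The primary comparison and the 47 per group are unaffected. This is a cheap improvement to the plan, not an error in its main conclusion.

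**What to change.** In section 8.3:

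1. Split the SBP and heart-rate AUC at each patient's mean baseline into area below and area above. Compare each with the planned linear model, adding the baseline value to the stratification factors. Section 7.2.2 already records both baselines. Area above may be zero for many patients, so the residual checks and transformations already foreseen in section 8.3 should be applied to it.
2. Report by arm, as a supportive outcome, the proportion of patients with a high-side SBP reading and the proportion with a high-side heart-rate reading. The analysis threshold is for the investigators to choose and to fix before data review. The cut-off matters: the 120% line in the illustration is only an example, and a higher line would flag fewer patients.
3. State that the total AUC describes average level and is to be read together with the two areas.

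The cost is wording only, since the one-minute readings and baselines are already collected. The downside is a few more secondary comparisons, which should be labelled supportive.
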